### 3.4 Patient reported outcome

PROs will be assessed using the EORTC QLQ-C30, EORTC QLQ-H&N35, CCI [REDACTED]. All items/questionnaires will be scored according to published scoring guidelines. All PRO analyses will be based on the full analysis set (FAS).

#### 3.4.1 EORTC QLQ-C30

The EORTC QLQ-C30 consists of 30 questions that can be combined to produce 5 functional scales (physical, role, cognitive, emotional, and social), 3 symptom scales (fatigue, pain, and nausea/vomiting), and a global measure of health status. The EORTC QLQ-C30 will be scored according to the EORTC QLQ-C30 scoring manual (Fayers et al 2001). An outcome variable consisting of a score from 0 to 100 will be derived for each of the symptom scales, each of the functional scales, and the global health status scale in the EORTC QLQ-C30 according to the EORTC QLQ-C30 Scoring Manual. Higher scores on the global health status and functioning scales indicate better health status/function, but higher scores on symptom scales represent greater symptom severity.

The change from baseline in HRQoL will be assessed using the EORTC QLQ-C30 global QoL scale, which includes 2 items from the EORTC QLQ-C30: “How would you rate your overall health during the past week?” (Item 29), and “How would you rate your overall QoL during the past week?” (Item 30).

#### Definition of clinically meaningful changes

Changes in score compared with baseline will be evaluated. A minimum clinically meaningful change is defined as an absolute change in the score from baseline of  $\geq 10$  for scales from the EORTC QLQ-C30 (Osoba et al 1998). For example, a clinically meaningful improvement in physical function (as assessed by EORTC QLQ-C30) is defined as an increase in the score from baseline of  $\geq 10$ , whereas a clinically meaningful deterioration is defined as a decrease in the score from baseline of  $\geq 10$ . At each post-baseline assessment, the change in symptoms/functioning from baseline will be categorized as improvement, no change or deterioration as shown in Table 10.

**Table 10 Change from BL and visit response for EORTC QLQ C30**

Score	Change from baseline	Visit response
EORTC QLQ-C30 Global quality of life score	$\geq +10$	Improvement
	$\leq -10$	Deterioration
	Otherwise	No change
EORTC QLQ-C30 symptom scales/items	$\geq +10$	Deterioration
	$\leq -10$	Improvement
	Otherwise	No change
EORTC QLQ-C30 functional scales	$\geq +10$	Improvement
	$\leq -10$	Deterioration
	Otherwise	No change

EORTC European Organisation for Research and Treatment of Cancer; QLQ-C30 30-item core quality of life questionnaire.

For each subscale, if <50% of the subscale items are missing, then the subscale score will be divided by the number of non-missing items and multiplied by the total number of items on the subscales (Fayers et al 2001). If at least 50% of the items are missing, then that subscale will be treated as missing. Missing single items are treated as missing. The reason for any missing questionnaire will be identified and recorded. If there is evidence that the missing data are systematic, missing values will be handled to ensure that any possible bias is minimized.

### Time to symptom deterioration

For each of the symptom scales in the EORTC QLQ-C30, time to symptom deterioration will be defined as the time from randomization until the date of the first clinically meaningful symptom deterioration (an increase in the score from baseline of  $\geq 10$ ) or death (by any cause) in the absence of a clinically meaningful symptom deterioration, regardless of whether the patient withdraws from study treatment or receives another anticancer therapy prior to symptom deterioration.

Patients whose symptoms (as measured by EORTC QLQ-C30) have not shown a clinically meaningful deterioration and who are alive at the time of the analysis will be censored at the time of their last PRO assessment where the symptom could be evaluated. Also, if symptoms deteriorate after two or more missed PRO assessment visits or the patient dies after two or more missed PRO assessment visits, the patient will be censored at the time of the last PRO assessment where the symptom could be evaluated (prior to the two missed assessment visits). If a patient has no evaluable visits or does not have baseline data they will be censored at 0 days. The population for the analysis of time to symptom deterioration will include a subset of the FAS who have baseline scores of  $\leq 90$ .

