For each subscale, if $< 50\%$ of the subscale items are missing, then the subscale score will be divided by the number of non-missing items and multiplied by the total number of items on the subscales (Fayers et al 1999). If at least 50% of the items are missing, then that subscale will be treated as missing. Missing single items are treated as missing. The reason for any missing questionnaire will be identified and recorded. If there is evidence that the missing data are systematic, missing values will be handled to ensure that any possible bias is minimized.

Time to symptom deterioration

For each of the symptoms scales in the EORTC QLQ-C30, time to symptom deterioration will be defined as the time from randomization until the date of the first clinically meaningful symptom deterioration (an increase in the score from baseline of ≥ 10) or death

(by any cause) in the absence of a clinically meaningful symptom deterioration, regardless of whether the patient discontinues study treatment or receives another anticancer therapy prior to symptom deterioration. Death will be included as an event only if the death occurs within 2 visits of the last PRO assessment where the symptom change could be evaluated.

Patients whose symptoms (as measured by EORTC QLQ-C30) have not shown a clinically meaningful deterioration and who are alive at the time of the analysis will be censored at the time of their last PRO assessment where the symptom could be evaluated. Also, if symptoms deteriorate after 2 or more missed PRO assessment visits or the patient dies after 2 or more missed PRO assessment visits, the patient will be censored at the time of the last PRO assessment where the symptom could be evaluated. If a patient has no evaluable visits or does not have baseline data they will be censored at 0 days. The population for the analysis of time to symptom deterioration will include a subset of the FAS who have baseline scores of ≤ 90 .

Time to quality of life/function deterioration

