For QoL, time to deterioration will be defined as the time from the date of randomization until the date of the first clinically meaningful deterioration (a decrease in the function scales or the global health status/QoL from baseline of ≥ 10) or death (by any cause) in the absence of a clinically meaningful deterioration, regardless of whether the patient discontinues study treatment or receives another anticancer therapy prior to QoL/function deterioration. Death will be included as an event only if the death occurs within 2 visits of the last PRO assessment where the QoL/function change could be evaluated.

Patients whose QoL (as measured by EORTC QLQ-C30) have not shown a clinically meaningful deterioration and who are alive at the time of the analysis will be censored at the time of their last PRO assessment where the QoL/function could be evaluated. Also, if QoL deteriorates after 2 or more missed PRO assessment visits or the patient dies after 2 or more missed PRO assessment visits, the patient will be censored at the time of the last PRO assessment where QoL/function could be evaluated. If a patient has no evaluable visits or does not have baseline data they will be censored at 0 days. The population for the analysis of time to QoL/function deterioration will include a subset of the FAS who have baseline scores of ≥ 10 .

Symptom improvement rate

The symptom improvement rate will be defined as the number (%) of patients with 2 consecutive assessments at least 14 days apart that show a clinically meaningful improvement (a decrease from baseline score ≥ 10 for EORTC QLQ-C30 symptom scales) in that symptom from baseline. The denominator will consist of a subset of the FAS who have a baseline symptom score ≥ 10 .

QoL/function improvement rate

The QoL/function improvement rate will be defined as the number (%) of patients with 2 consecutive assessments at least 14 days apart that show a clinically meaningful improvement (an increase from baseline score ≥ 10 for EORTC QLQ-C30 functional scales and global health status/QoL) in that scale from baseline. The denominator will consist of a subset of the FAS who have a baseline QoL/function score ≥ 10 .

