If the patient has no evaluable visits or does not have baseline data, they will be censored at Day 1 unless they die within 2 consecutive visits of baseline, then they will be treated as an event with date of death as the event date.

The PFS time will always be derived based on scan/assessment dates and not visit dates.

RECIST 1.1 assessments/scans contributing toward a particular visit may be performed on different dates. The following rules will be applied:

- For Investigator assessments, the date of progression will be determined based on the earliest of the RECIST 1.1 assessment/scan dates of the component that indicates progression.
- For BICR assessments, date of progression will be determined from the progression date (PROGSCDT) provided by the BICR progression scan dates (PROGSCDT) dates.
- When censoring a patient for PFS, the patient will be censored at the latest of the dates contributing to a particular overall visit assessment.

**Note:** For target lesions, only the latest scan date is recorded out of all scans performed at that assessment for the target lesions, and similarly for non-target lesions, only the latest scan date is recorded out of all scans performed at that assessment for the non-target lesions.

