### Time to symptom deterioration

For each of the symptom scales/items in the H&N35, time to symptom deterioration will be defined as the time from randomization until the date of the first clinically meaningful symptom deterioration (an increase in the score from baseline of  $\geq 10$ ) or death (by any cause) in the absence of a clinically meaningful symptom deterioration, regardless of whether the patient withdraws from study treatment or receives another anticancer therapy prior to symptom deterioration. Death will be included as an event only if the death occurs within 2 visits of the last PRO assessment where the symptom change could be evaluated.

Patients whose symptoms (as measured by the H&N35) have not shown a clinically meaningful deterioration and who are alive at the time of the analysis will be censored at the time of their last PRO assessment where the symptom could be evaluated. Also, if symptoms progress after 2 or more missed PRO assessment visits or the patient dies after 2 or more missed PRO assessment visits, the patient will be censored at the time of the last PRO assessment where the symptom could be evaluated. If a patient has no evaluable visits or does not have baseline data, they will be censored at 0 days. The population for analysis of time to symptom deterioration will include a subset of the FAS population who has baseline scores  $\leq 90$ .

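### QLQ-C30 time to deterioration: the SAP counts death as an event, yet censors at day 0 a patient who dies before any post-baseline form

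*SAP*

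**What the plan says.** SAP 3.4.1 defines QLQ-C30 time to symptom deterioration as the time from randomization to the first meaningful worsening, or to "death (by any cause) in the absence of a clinically meaningful symptom deterioration". A death is censored, at the last evaluable questionnaire, if "the patient dies after two or more missed PRO assessment visits". The paragraph then says: "If a patient has no evaluable visits or does not have baseline data they will be censored at 0 days". The HRQoL/function paragraph of the same section has the same three elements.

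SAP 3.4.2 (QLQ-H&N35) has an equivalent day-0 sentence, "If a patient has no evaluable visits or does not have baseline data, they will be censored at 0 days", and also a condition on death: "Death will be included as an event only if the death occurs within 2 visits of the last PRO assessment where the symptom change" (the sentence ends by requiring that this change was assessable).

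Protocol 8.4.3.1 and 8.4.3.2 contain the day-0 rule for both instruments. They also put the death condition on both: for QLQ-C30 symptoms, "Death will be included as an event only if the death occurs within 2 visits of the last PRO assessment" at which change could be evaluated, and for QLQ-C30 QoL/function, "within 2 visits of the last PRO assessment where the QoL/function change could be evaluated". SAP 3.4.1 does not carry this condition.

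The PFS rule in SAP 3.2.1.1 also censors patients with no evaluable visits or no baseline, but adds an exception: "unless they die within 2 consecutive visits of baseline, then they will be treated as an event with date of death as the event date". Protocol 8.4.1.3 has the same exception for PFS. No PRO section has one.

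**The concern.** Take a patient with a baseline QLQ-C30 score who dies in week 6. The first post-baseline form is not due until week 8, so no visit has been missed. Under the event definition and the missed-visit rule in SAP 3.4.1, the death is an event on its date. Under the day-0 sentence the same patient contributes nothing. SAP 3.4.1 does not say which rule prevails, so two programmers could each follow the text and get different event counts and curves.

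Dropping the protocol's death condition from SAP 3.4.1 sharpens the conflict, because that condition would have pointed to one answer. It also leaves QLQ-C30 and H&N35 with different death rules inside one SAP.

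Five secondary PRO endpoints are affected in one way or the other: global health status, physical function and fatigue (QLQ-C30), and pain and swallowing (H&N35). SAP 4.2.12 tests them at 1% for MEDI4736 versus SoC.

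**Working it through.** **Reading the rules for one patient: baseline score present, no post-baseline form, death before two forms are missed.**

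| Text | Death condition | Missed-visit rule | Day-0 sentence | Result |
|---|---|---|---|---|
| SAP 3.4.1 (both QLQ-C30 endpoints) | none; any death is an event | does not apply | applies | contradictory |
| SAP 3.4.2 (H&N35) | not met: no assessment at which change could be evaluated | does not apply | applies | censored at day 0 |
| Protocol 8.4.3.1, 8.4.3.2 | not met, same reason | does not apply | applies | censored at day 0 |
| SAP 3.2.1.1 (PFS) | exception for early death | – | exception overrides | event |

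Could the baseline form count as an evaluable visit, so that the day-0 sentence does not reach this patient? That would leave the sentence with almost nothing to do. It lists missing baseline data separately, and the analysis is already restricted to patients with a qualifying baseline score (at most 90 for symptoms, at least 10 for function). Its working content is the patient with a baseline form and nothing after it.

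**How many patients.** The documents give no event count or power for the PRO endpoints, so there is no stated figure to reproduce. Inputs:
- SoC survival: median 10.1 months, 12% alive at 24 months (SAP 1.3).
- 190 patients per arm for monotherapy and SoC; 86 per arm in the PD-L1 TC/IC high subgroup (SAP Table 5).
- First post-baseline form 8 weeks (QLQ-C30) or 4 weeks (H&N35) after Cycle 1 Day 1 (Protocol Tables 2 and 3).

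Weibull through both survival inputs:
- shape = ln[ln(1/0.12)/ln 2] / ln(24/10.1) = 1.292
- scale = 10.1/(ln 2)^(1/1.292) = 13.41 months
- P(dead by t) = 1 − exp[−(t/13.41)^1.292]

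| First form | t (months) | P(dead) | of 190 | of 86 |
|---|---|---|---|---|
| Day 28 (H&N35) | 0.92 | 3.1% | 5.9 | 2.7 |
| Day 56 (QLQ-C30) | 1.84 | 7.4% | 14.1 | 6.4 |

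Dosing may start up to 5 working days after randomization (taken as 7 days) and forms have a ±3-day window. Days 25 to 38 give 2.7–4.6%, and days 53 to 66 give 6.9–9.1%. An exponential through the median alone gives 6.1% and 11.9%, but it leaves 19% alive at 24 months against the planned 12%, so the Weibull is preferred.

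**Effect on the hazard ratio.** Simulation with 190 per arm, 17-month accrual, cut-off at 40.6 months and equal deterioration in both arms (assumed median 200 days, detected at the next form). The death hazard on immunotherapy is multiplied for the first 3 months only; the multipliers are assumptions.

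| Multiplier | QLQ-C30: death as event vs day 0 | log-HR shift | H&N35: death as event vs day 0 | log-HR shift |
|---|---|---|---|---|
| 1 | 1.00 vs 1.00 | 0 | 1.00 vs 1.00 | 0 |
| 1.5 | 1.06 vs 1.03 | 0.03 | 1.06 vs 1.05 | 0.01 |
| 2 | 1.13 vs 1.06 | 0.07 | 1.12 vs 1.09 | 0.03 |

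The standard error of the log hazard ratio is 0.105–0.110, so the 99% half-width is 2.576 × 0.105 to 2.576 × 0.110 = 0.27 to 0.28. The largest shift is 0.067/0.110 = 0.6 of a standard error. Assumed deterioration medians of 120 or 300 days leave the shifts at a multiplier of 2 essentially unchanged (0.066–0.069 and 0.026–0.028). A separate simulation using the exponential curve, which has more early deaths, gave 1.18 vs 1.05–1.06 for QLQ-C30 at a multiplier of 2, so the size depends on the assumed curve.

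**The case against.** The strongest reply is that the day-0 sentence is specific and comes last, so it should override the general event definition. It also gives the result that the protocol's death condition implies. On that view SAP 3.4.1 merely lost one protocol sentence. This has force as a guess at intent. But the SAP does not state that precedence, and the missed-visit rule beside it is just as specific about which deaths are censored. The conflict in SAP 3.4.1 therefore stands.

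The reply succeeds for H&N35 and the protocol. A reader might infer that every PRO endpoint is self-contradictory. The documents do not support that: where death counts only within two visits of an assessment at which change could be evaluated, a patient with no such assessment fails the condition, and the day-0 sentence agrees.

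It is also fair that nothing obliges the PRO endpoints to follow the PFS rule. Limiting deaths to patients with an evaluable change is a coherent choice for a symptom endpoint. The proposed exception is therefore a real change for H&N35.

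A reader might also infer that the rule favours immunotherapy. Protocol 1.2.5 describes an apparent excess of early deaths with this drug class but gives no rate. The plan's own sizing assumes no separation of the OS curves for 3 months, and then the hazard ratio is the same either way.

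SAP 4.2.12 mentions multiple imputation and pattern-mixture models if missing data are substantial. That is optional and does not decide whether a known death is an event. Nor can one say that dropping the clause went unrecorded, because the entry in SAP section 6 is redacted.

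**Conclusion.** The point holds in a limited form and is minor. SAP 3.4.1 gives two incompatible instructions for a QLQ-C30 patient who has a baseline score and no later form and dies before missing two visits. For H&N35 there is no firm contradiction; early deaths leave the analysis at day 0, and the two instruments differ in their death rule.

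About 14 of 190 patients per arm (QLQ-C30) and 6 of 190 (H&N35) are involved. These counts assume the Weibull planning curve in both arms, a qualifying baseline score for everyone, and a returned first form from every survivor. Patients who skip the first form and die before the second face the same rules but are not counted, because no return rate is given.

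Event counts and Kaplan-Meier curves change with the reading in any case. The hazard ratio moves only if early mortality differs between arms, and on this curve by at most about 0.6 of a standard error even at an assumed doubling. The endpoints are supportive and outside the multiple testing procedure. OS is untouched.

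**What to change.** 1. In SAP 3.4.1, for both QLQ-C30 endpoints, add to the day-0 sentence: *unless the patient has a baseline score and dies within two scheduled PRO visits of baseline, in which case death is an event on the date of death*. This follows the PFS rule in SAP 3.2.1.1.
2. State whether the protocol's two-visit condition on death applies to QLQ-C30.
3. In SAP 3.4.2, apply the same rule to H&N35 by stating that the baseline form counts as the last PRO assessment when there is no post-baseline form.
4. Record this in SAP section 6 as a change from Protocol 8.4.3.1 and 8.4.3.2, or amend those sections to match. For H&N35 it alters the rule and should be presented as such.

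The cost is one sentence in three places, one clarifying phrase on the death condition, a change-log entry and a small programming change. No new data are needed.

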### **Time to HRQoL/Function deterioration**

For HRQoL, time to deterioration will be defined as the time from the date of randomization until the date of the first clinically meaningful deterioration (a decrease in the function scales or the global health status/QoL from baseline of  $\geq 10$ ) or death (by any cause) in the absence of a clinically meaningful deterioration, regardless of whether the patient withdraws from study treatment or receives another anticancer therapy prior to HRQoL/function deterioration.

Patients whose HRQoL (as measured by EORTC QLQ-C30) have not shown a clinically meaningful deterioration and who are alive at the time of the analysis will be censored at the time of their last PRO assessment where the HRQoL/function could be evaluated. Also, if HRQoL deteriorates after two or more missed PRO assessment visits or the patient dies after 2 or more missed PRO assessment visits, the patient will be censored at the time of the last PRO assessment where HRQoL/function could be evaluated. If a patient has no evaluable visits or does not have baseline data they will be censored at 0 days. The population for the analysis of time to HRQoL/function deterioration will include a subset of the FAS who have baseline scores of  $\geq 10$ .

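### After two or more missed PRO visits, the SAP limits censoring to the last form before the gap for QLQ-C30 symptoms only; the function/global QoL and H&N35 rules lack that limit and, read literally, censor at or after the form that shows the deterioration.

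*SAP*

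**What the plan says.** Three time-to-deterioration rules in the SAP share one trigger: deterioration or death after two or more missed PRO visits.

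- **QLQ-C30 symptom scales (SAP 3.4.1, Time to symptom deterioration).** The patient is "censored at the time of the last PRO assessment where the symptom could be evaluated (prior to the two missed assessment visits"). The date is tied to the period before the gap.
- **QLQ-C30 function scales and global health status (SAP 3.4.1, Time to HRQoL/Function deterioration).** The trigger is "if HRQoL deteriorates after two or more missed PRO assessment visits", and then "the patient will be censored at the time of the last PRO assessment where HRQoL/function could be evaluated". Nothing ties the date to the period before the gap.
- **QLQ-H&N35 (SAP 3.4.2, Time to symptom deterioration).** The trigger is "Also, if symptoms progress after 2 or more missed PRO assessment visits". The consequence reads "the patient will be censored at the time of the last PRO assessment where the symptom could be evaluated. If a patient has no", where the quoted text already passes to a separate rule for missing data. Again there is no limit.

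The analysis sections (SAP 4.2.12, 4.2.12.1 and 4.2.12.2) do not supply the missing limit. The protocol has it for none of the three: section 8.4.3.1 refers to "the last PRO assessment where the symptom could be evaluated. If a patient has no evaluable visits" for symptoms and says "the patient will be censored at the time of the last PRO assessment where QoL/function could be evaluated" for function, and section 8.4.3.2 is worded likewise for H&N35. So the SAP added the limit to one of three parallel rules. For PFS, SAP 3.2.1.1 does state that censoring goes back to the last evaluable RECIST assessment before the two missed visits.

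**The concern.** The usual reason to censor before a gap is that the time of an event first seen after a long unobserved stretch is unknown, so follow-up stops where the patient was last known to be event-free. The wording for function/QoL and H&N35 does not achieve this in the deterioration branch. A patient can be found to have deteriorated after the gap only because an evaluable form exists after the gap. The last evaluable form is then that form or a later one. Read literally, the patient contributes event-free time across the unobserved stretch and up to, or beyond, a recorded deterioration.

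SAP 4.2.12 names five secondary PRO endpoints. Four fall under the unlimited wording: global health status, physical function, H&N35 pain and H&N35 swallowing. Fatigue alone has the limit. Fatigue and physical function come from the same QLQ-C30 form, so one patient with one gap can be censored months apart on the two scales. Two programmers could also implement four of the five endpoints differently, and each could point to the text.

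**Working it through.** **Inputs.** QLQ-C30 is completed every 8 weeks and QLQ-H&N35 every 4 weeks, counted from Cycle 1 Day 1 (Protocol Tables 2 and 3). The form patterns below are assumed for illustration.

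**Number of missed visits.** Missed visits = (week of first deterioration − week of last earlier form) / interval − 1.

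- QLQ-C30, forms at weeks 0, 8 and 32, first deterioration at week 32: (32 − 8)/8 − 1 = 2. The rule is triggered.
- H&N35, forms at weeks 0, 4 and 16, first deterioration at week 16: (16 − 4)/4 − 1 = 2. The rule is triggered.

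**Censoring date under each wording.**

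| Case | With the limit | Without it, read literally | Extra event-free time |
|---|---|---|---|
| QLQ-C30, no later form | week 8 | week 32 | 32 − 8 = 24 weeks |
| QLQ-C30, one more form at week 40 | week 8 | week 40 | 40 − 8 = 32 weeks |
| H&N35, no later form | week 4 | week 16 | 16 − 4 = 12 weeks |
| H&N35, one more form at week 20 | week 4 | week 20 | 20 − 4 = 16 weeks |

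**Death branch.** If the patient dies after the gap and no evaluable form follows it, the last evaluable form is already the one before the gap. The two wordings then give the same date.

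**Role of the endpoints.** Five endpoints with a Bonferroni adjustment: 0.05/5 = 0.01, which reproduces the 1.0% level and 99% intervals in SAP 4.2.12. Four of the five use the unlimited wording.

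**Size.** The documents give no rate of two-form gaps, so every figure here is conditional.

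- *Gaps common.* Assume median time to deterioration of 5 to 10 months and a single two-form gap in 30% to 60% of patients who have at least four scheduled forms. Across simulations that differed in how long forms continue to be collected, the wording changed the censoring date in about 2% to 12% of patients. In those patients the mean shift was about 7 to 13 months where it was recorded. The deterioration-free proportion at 9 months rose by roughly 1 to 6 points.
- *Missingness sparse.* Assume each form is missed independently with probability 15%, a figure suggested by the 85% compliance level at which Protocol 5.3.2 recommends a check-in call. Then 1% to 2% of patients change and the 9-month proportion rises by about 1 point.
- *Hazard ratio.* With equal gap rates in the two arms, the HR was essentially unchanged (within 0.02). With an assumed 30% in one arm and 60% in the other, it moved by 0.03 to 0.12. The movement can go either way: the arm with more gaps gains the spurious event-free time.

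**The case against.** The strongest reply is that this is loose drafting and not a planned rule. The neighbouring sentence on the same questionnaire and the PFS rule both look back to before the gap. The H&N35 text (and, for QLQ-C30, Protocol 8.4.3.1) also uses a similar phrase for the form that precedes a death. On that reading the intended date is clear from context. Much of this stands, and the omission is probably a slip. It does not settle the matter, because the limit is written for one scale and absent from the next paragraph, and a programmer may take that difference as deliberate.

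The affected branch is also narrow. It needs two consecutive missed forms, a later evaluable form, and first deterioration on that later form. That stands too.

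The plan has partial safeguards: compliance by visit, a commitment to limit bias if missingness is systematic (SAP 3.4.1), and multiple imputation or pattern-mixture models that may be explored (SAP 4.2.12). These bear on missing data in general and do not change the censoring date.

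A reader might infer more than the documents support:

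- *That the PRO hazard ratios are biased.* This needs gap rates that differ by arm. The open-label design makes a difference plausible, but nothing in the documents gives the rates or says which arm would have more gaps.
- *That retreatment worsens the problem.* SAP 4.1 includes retreatment data in all PRO analyses, but only combination-arm patients can be retreated (Protocol 7.2.3). The comparison tested at 1.0% is MEDI4736 versus SoC, so it is not touched.
- *That the trial's main conclusions are at risk.* These endpoints are supportive and outside the multiple testing procedure, and the OS analyses do not use this rule.

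**Conclusion.** The point holds as a defect of wording that, followed literally, gives a wrong censoring date. It leaves four of the five secondary PRO endpoints on a different rule from fatigue, and for the affected patients it credits event-free time up to or past a recorded deterioration. In the worked examples the excess is 24 to 32 weeks for QLQ-C30 function and 12 to 16 weeks for H&N35.

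The consequence is limited. It touches supportive endpoints only, in one branch of the rule. The likely effect is a somewhat high deterioration-free curve in each arm, by an amount that depends on gap rates the documents do not give. Any shift in the HR is hypothetical and its direction cannot be stated. The text should be corrected because the cost is negligible and it removes two competing implementations, not because a material bias has been shown.

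**What to change.** Before database lock, add the parenthetical limit that ends "the last PRO assessment where the symptom could be evaluated (prior to the two missed assessment visits") to the censoring sentences for HRQoL/function in SAP 3.4.1 and for H&N35 in SAP 3.4.2, so that all scales follow the QLQ-C30 symptom rule. A documented SAP amendment is enough; Protocol 8.1 allows amendments up to reporting. Protocol 8.4.3.1 and 8.4.3.2 can be aligned if the protocol is amended for other reasons.

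The cost is a few words, a check of the derivation program, and earlier censoring for a small number of patients. The corrected rule still sets aside the deterioration seen after the gap, so it reduces informative censoring but does not remove it.
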